The study will also include a multidisciplinary survey of awareness regarding the issue of urinary tract dilation diseases. Specialists from the fields of pediatrics, neonatology, pediatric nephrology, pediatric nephrology, gynecology, ultrasound in gynecology and obstetrics, or radiology will be approached by filling in a short questionnaire created via docs.google.com, in which we will find out information about the methods used for prenatal and postnatal diagnosis of dilations urinary tract, the method of classifying these anomalies and their subsequent solution.

Questionnaire for gynecologists, prenatal sonographers:

1. Do you encounter dilation of the urinary tract in fetuses in your practice?
 - a) Yes, often.
 - b) Sporadic.
 - c) Rarely, almost never.
2. In case of US finding of dilation of the urinary tract in the second or third trimester:
 - a) I will only describe the given anomaly descriptively.
 - b) I will classify the anomaly in the classification system.
3. When describing the anomaly, do you use terms such as "pyelectasis, pelviectasis, hydronephrosis"?
 - a) Yes.
 - b) No.
4. If you use a classification in the evaluation of dilations of the urinary tract, which one?
 - a) SFU classification system (Society for Fetal Urology Grading system).
 - b) UTD (Urinary Tract Dilation) classification system.
 - c) I don't use any.
5. If dilatation of the urinary tract is found in the third trimester, do you recommend a pregnant woman to be checked by a pediatric nephrologist after birth?
 - a) Yes.
 - b) No.
 - c) I will instruct her to mention the finding as part of the newborn USG screening.
6. Are you informed about the postnatal finding in a child with prenatally diagnosed dilation of the urinary tract?
 - a) Yes, I will ask the pregnant woman to inform me about the child's examinations.
 - b) Yes, I work with a pediatric nephrologist who sends me the findings.
 - c) No, it is not in my interest.

7. Do you think that the system of care for a patient (fetus, child) with dilatation of the urinary tract is sufficient in our country?

a) After the prenatal diagnosis of dilation of the urinary tract, I do not deal with the management of the fetus and the child.

b) It is not sufficient, there are no standards in prenatal care for a fetus with dilation of the urinary tract.

c) The current management system for excretory system anomalies and dilatations is sufficient.

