a) It is not sufficient, the standards in prenatal and postnatal care of a patient with dilation of the urinary tract are insufficient.

b) The current management system for excretory system anomalies and dilatations is sufficient.

9. Would we welcome greater cooperation between specialists (gynecologist, neonatologist, pediatrician, pediatric urologist, pediatric nephrologist) in the diagnosis and treatment of a patient (fetus, child) with dilation of the urinary tract?

a) Yes, it is necessary.

b) No, as it is now, it is sufficient.

c) I can't judge it.

Study

Inclusion criteria of cases in the study:

1. Singleton pregnant women whose fetuses were diagnosed with dilation of the urinary tract as an isolated US finding before the 28th week of pregnancy. Dilation of the urinary tract was categorized according to the 2014 UTD classification system.
2. Fetal patients with subsequent US control in the third trimester after the 28th week of pregnancy.
3. Newborns and children with prenatally diagnosed UTD, which, depending on the severity, required a postnatal examination by a pediatric nephrologist within a month after birth and then in his follow-up up to 6 months after birth.

Exclusion criteria:

Multiple pregnancies, UTD diagnosed only in the third trimester, associated anomalies of other organs, aneuploidy, newborns and children monitored by someone other than a selected pediatric nephrologist, patients who were lost from follow-up (did not come for recommended control, etc.).

Study population:

Approximately 4,000 morphological ultrasound examinations of fetuses are performed annually at the SonoClinic and Emporia workplaces. Approximately 60-80 cases of dilation of the urinary tract are detected annually. In 80% of them there is a complete adjustment before delivery, the remaining approximately 20% have persistent dilation of the urinary tract with varying degrees of severity (UTD A1 – low risk, UTD 2-3 – high risk). According to the recommendations of the UTD classification, these fetuses are subsequently recommended for postnatal examination by a pediatric nephrologist. The estimated number of cases with dilation of the urinary tract for analysis postnatally will be 180 to 230.

Demographics:

Age, parity, occurrence of urinary tract anomalies in the child's father and siblings, sex of the fetus, method of conception.

Study design:

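### The two survey forms ask the same question about whether care is sufficient but offer answers that do not match, so the shares answering 'not sufficient' do not measure the same thing

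*Protocol*

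**What the plan says.** The section Methodology of study, under Multidisciplinary survey on awareness, prints two questionnaires: one for gynecologists and prenatal sonographers (the prenatal form, 10 items) and one for pediatricians, neonatologists, pediatric urologists and nephrologists, and radiologists (the postnatal form, 9 items).

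Item 7 of the prenatal form and item 8 of the postnatal form share one stem: "Do you think that the system of care for a patient (fetus, child) with dilatation of the urinary tract is sufficient in our country".

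The prenatal form offers three answers:
- Option (a) describes what the respondent does once the diagnosis is made: "I do not deal with the management of the fetus and the child".
- Option (b) is the unfavourable answer and names a reason: "It is not sufficient, there are no standards in prenatal care for a fetus with dilation of the urinary tract".
- Option (c) is the favourable answer, with no reason attached.

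The postnatal form offers two:
- Option (a) is again the unfavourable answer, with a wider reason: "It is not sufficient, the standards in prenatal and postnatal care of a patient with dilation of the urinary tract are insufficient".
- Option (b) repeats the favourable sentence of the prenatal form word for word.

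The next item on the postnatal form, item 9, concerns cooperation ("Would we welcome greater cooperation between specialists") and includes the answer "I can't judge it". Item 7 of that form also has a no-comment answer, as does item 9 of the prenatal form. The cooperation item is not on the prenatal form.

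**The concern.** Goal 1 is a multidisciplinary picture of awareness, diagnosis and management. This is the one question put to both groups in the same words about whether national care is adequate, so a reader of the results will naturally set the two percentages side by side. Three features of the printed answers stand in the way:

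- On the prenatal form, option (a) answers a different question. Role and opinion are separate facts, and the item records only the role for anyone who ticks (a).
- On the postnatal form, a respondent without a view has no option that says so, and cannot later be told apart from one who holds a view.
- The unfavourable answer carries a built-in reason, and the reason differs. A gynecologist who thinks only postnatal care falls short has no matching answer, although the stem covers fetus and child.

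These are properties of the instrument. An analysis plan can choose a denominator, but it cannot recover opinions that were not recorded.

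**Working it through.** **Comparison of the printed answers**

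| Feature | Prenatal form, item 7 | Postnatal form, item 8 |
|---|---|---|
| Stem | same | same |
| Sufficient | yes, (c) | yes, (b), same sentence |
| Not sufficient | yes, (b): prenatal standards absent | yes, (a): prenatal and postnatal standards inadequate |
| Third answer | (a): not involved in management | none |
| No-opinion answer elsewhere on the form | item 9 | items 7 and 9 |

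**Size of the effect**

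The protocol gives no number of survey respondents and no expected share, so there is no planned figure to reproduce. The calculation below is an illustration. Its inputs are assumptions and are set equal in both groups, so that true opinion does not differ:
- p = share saying not sufficient among those with a view
- q = share with no view or not involved
- s = share of the q group who choose not sufficient when only two answers are available.

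It also assumes that all of the q group on the prenatal form, and nobody else, tick (a), that everyone on the postnatal form answers, and that the two wordings of not sufficient are read alike.

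Formulas:
- Prenatal form, all respondents: (1 − q)·p
- Prenatal form, leaving out (a): p
- Postnatal form: (1 − q)·p + q·s
- Gap, postnatal minus prenatal with (a) kept: q·s
- Gap, postnatal minus prenatal with (a) left out: (1 − q)·p + q·s − p = q·(s − p)

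*Case of no distortion.* If (a) is left out and every postnatal respondent holds a view (q = 0 on that form), both forms give p and the gap is 0.

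*p = 0.70, q = 0.20.* Prenatal form: 0.80 × 0.70 = 56% of all respondents, 70% without (a). Postnatal form: 0.56 + 0.20·s, which is 56%, 66% or 76% at s = 0, 0.5 or 1. Against 70%, the gap is −14, −4 or +6 points.

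*p = 0.70, q = 0.40.* Prenatal form: 0.60 × 0.70 = 42%, or 70% without (a). Postnatal form: 0.42 + 0.40·s, which is 42%, 62% or 82%. Against 70%, the gap is −28, −8 or +12 points.

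*Range over p = 0.5 to 0.9, q = 0.1 to 0.4, s = 0 to 1.* With (a) kept, the gap runs from 0 to q, so at most 40 points. With (a) left out, it runs from 0.4 × (0 − 0.9) = −36 points to 0.4 × (1 − 0.5) = +20 points.

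Leaving out (a) therefore removes the distortion only when the postnatal group has no undecided respondents, or when those respondents happen to split as the others do (s = p). The postnatal form cannot show whether either holds. The difference in meaning between the two unfavourable answers comes on top and is not in these figures.

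**The case against.** The strongest reply is that the protocol nowhere says this item will be compared or pooled across disciplines. It prints separate forms for separate audiences, which is a legitimate design, and each can be reported alone. Tabulation may also be settled in an analysis plan that is not shown. This stands: the comparison is inferred from the identical stem and the multidisciplinary goal. Reporting by form still does not supply the opinions hidden behind (a) or identify undecided respondents on the postnatal form.

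Some stronger readings are tempting but not supported:

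- *That the forms by themselves create a large gap.* Suppose 60% of those with a view call care insufficient and 10%, 30% or 50% of prenatal respondents tick (a). With (a) in the denominator the prenatal form shows 0.60 × 0.90 = 54%, 0.60 × 0.70 = 42% or 0.60 × 0.50 = 30%, against 60%. But (a) is recorded separately. Leaving it out returns 60% against 60%, so a gap of 6 to 30 points is no firm estimate of harm.
- *That respondents are compelled to choose.* The protocol says only that the questionnaire is an online form. It does not state that answers are required or that only one may be ticked. The lettered layout suggests single choice but does not establish it.
- *That the proposed care model rests on this item.* Goal 3 does not mention the survey, and the Introduction places the model after both the survey and the cohort work.
- *That leaving the cooperation item off the prenatal form is a defect.* Items 5 and 6 of that form already ask about referral to, and feedback from, a pediatric nephrologist. They record practice, not a wish for more cooperation, so they are not the same item, but the topic is covered.

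**Conclusion.** The mismatch is real and can be read directly from the two forms. The same question is asked with answers that differ in number, in whether they address the question, and in the reason attached to not sufficient. As printed, the prenatal form loses the view of anyone who ticks only (a), the postnatal form cannot identify those without a view, and any cross-group or overall not-sufficient share would mix different meanings.

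The size cannot be derived from the documents. Under equal opinions and equal reading of the two wordings, it is zero if (a) is left out and all postnatal respondents hold a view. Otherwise it depends on the unknown share without a view, and the illustrated ranges rest wholly on assumed values.

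The point is minor. It concerns one of 19 printed items (10 + 9), bears on goal 1 only, and leaves the primary goal of predicting a severe postnatal course and surgery untouched. It does not show that the sponsor plans an invalid comparison.

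**What to change.** Print one identical item on both forms with three answers: sufficient, not sufficient, cannot judge. Ask separately, on both forms, whether the respondent takes part in management after the diagnosis. Ask the reason for not sufficient separately too, with the same list on both forms (prenatal standards, postnatal standards, other). When true opinions are equal, both forms then estimate the same quantities, (1 − q)·p over all respondents and p among those with a view, so the gap due to the forms is 0 whatever p, q and s are.

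The study start is given as January 2023 and the protocol is dated 19.12.2023, so some answers may already have been collected. Report those by form, show option (a) as its own category, state the difference in wording, and do not pool them across forms or with answers to the revised item.

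The cost is an edit of the online forms and keeping old and new answers apart, with fewer answers in each set. Adding the cooperation item to the prenatal form is optional.

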Despite the obvious advantages, the UTD classification is generally not often used in clinical practice. It is most commonly used by pediatric radiologists. Only 19% of pediatric urologists use this system compared to 70% of those who use the SFU scoring system despite UTD showing higher reliability (Gray, 2022). Also, a literature review between 2017 and 2019 confirmed that only 6% of studies use the UTD classification system, while 37% use the SFU grading system and 33% use the APRPD system. Interestingly, approximately 20% of studies do not use any scoring system when describing urinary tract dilations in children (Suson, 2020). While the authors, members of pediatric radiology, created a computer application as a training aid for teaching the UTD classification system, which can be shared and used at any time (Maizels, 2017).

There are several reasons for the less-than-expected use of the UTD classification system. Complexity described by some departments, lack of information between departments, as the system was created for multidisciplinary cooperation, incompleteness (classification is always based on the presence of intrarenal dilation, does not take into account isolated dilatations of the ureter or other anomalies of the urinary tract, which is gradually being modified), impossibility to predict some dilatational anomalies of the urinary tract, such as vesicoureteral reflux, as well as national or international standards that have not yet been developed in many countries (Nguyen 2022).

The UTD classification system proposes a unified evaluation system for prenatal and postnatal dilative diseases of the urinary tract. A review of available studies and literature showed that the system can predict the clinical consequences of the disease and has better inter- and intraobserver reliability compared to other systems. The goal is to increase awareness of this system among specialties and create standardized management plans for the patient with dilated urinary tract disease (Green 2022, Nguyen 2022).

Methodology of study

Multidisciplinary survey on awareness

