8. Have you encountered or do you use the prenatal UTD classification system (2014) when evaluating dilations of the urinary tract?

a) Yes.

b) No.

9. Do you think that the UTD classification system is optimal for prenatal and postnatal management of a patient with urinary tract dilatation?

a) Yes, it is usable in practice in risk stratification in fetuses with UTD.

b) No, it is too complex and does not cover all dilative diseases of the urinary tract.

c) I can't comment on that.

10. What are the normal values of renal pelvis width (APRPD) in the second, third trimester and postnatally?

a) 4-7 mm, 7-10 mm, over 10 mm

b) Up to 4 mm, 4-7 mm, 10 mm

c) 4-5 mm, 7-8 mm, 10 mm

Questionnaire for pediatricians, neonatologists, pediatric urologists and nephrologists, radiologists:

1. In your practice, do you encounter a patient with dilation of the urinary tract?

a) Yes, often.

b) Sporadic.

c) Rarely, almost never.

2. In case of US finding of dilation of the urinary tract in a child:

a) I will only describe the given anomaly descriptively.

b) I will classify the anomaly in the classification system.

3. When describing the anomaly, do you use terms such as "pyelectasis, pelviectasis, hydronephrosis"?

a) Yes.

b) No.

4. If you use a classification system when evaluating urinary tract dilations, which one?

a) SFU classification system (Society for Fetal Urology Grading system).

b) UTD (Urinary Tract Dilation) classification system.

b) I don't use any.

5. When examining a child with dilatation of the urinary tract, are you interested in prenatal findings?

a) Yes, I am interested in the finding and its severity in the prenatal period.

b) It is not useful information for me

c) Sometimes I ask the patient about it, or she reports it to me herself.

6. Have you encountered or are you using the postnatal UTD classification system (2014) when evaluating dilations of the urinary tract?

a) Yes.

b) No.

7. Do you think that the UTD classification system is suitable for the prenatal and postnatal management of a patient with urinary tract dilation?

d) Yes, it is applicable in practice in risk stratification in a patient with UTD.

e) No, it is too complex and does not cover all dilative diseases of the urinary tract.

f) I can't comment on that.

8. Do you think that the system of care for a patient (fetus, child) with dilatation of the urinary tract is sufficient in our country?

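### The only No answer on the UTD system joins two separate objections on both survey forms, and on the gynecologists' form Yes says less than its question asks

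*Protocol*

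**What the plan says.** The protocol prints both questionnaires in full, with fixed answers.

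- **Gynecologists and prenatal sonographers, item 9.** Question: "Do you think that the UTD classification system is optimal for prenatal and postnatal management of a patient with urinary tract dilatation". Positive answer: "Yes, it is usable in practice in risk stratification in fetuses with UTD".
- **Pediatricians, neonatologists, pediatric urologists and nephrologists, radiologists, item 7.** Question: "Do you think that the UTD classification system is suitable for the prenatal and postnatal management of a patient with urinary tract dilation". Positive answer: "Yes, it is applicable in practice in risk stratification in a patient with UTD".
- **Both items.** The single negative answer is "No, it is too complex and does not cover all dilative diseases of the urinary tract", and the third answer is "I can't comment on that". Neither item shows an other-reason answer or a free-text field.

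The Review of the literature explains why UTD is used less than expected. Its list opens with "Complexity described by some departments, lack of information between departments, as the system was created for multidisciplinary cooperation, incompleteness" and goes on to the system's failure to predict some anomalies and the absence of standards in many countries. Incompleteness has its own explanation there: the scheme starts from dilation inside the kidney and leaves out isolated dilation of the ureter.

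The survey is the first listed scientific goal. The section on the survey gives its content as the methods of diagnosis in use, the way anomalies are classified, and what is done next.

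**The concern.** The negative answer has two parts joined by *and*. The protocol itself treats the parts as different reasons, and a respondent can hold either without the other. Someone who finds UTD simple but knows that it omits isolated ureteral dilation must either sign up to a complexity complaint they do not hold or choose an answer that hides the limit they see. Someone who finds it complete but complicated is in the same position.

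Item 9 has a second fault. Its question is strong and broad, while its Yes is weaker and narrower. A gynecologist who thinks UTD usable but not optimal fits neither Yes nor No.

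These are the only items on which specialists judge UTD itself. If the two objections cannot be told apart, the survey cannot say whether rejection comes from difficulty of use or from gaps in the scheme. Those call for different responses: training for the first, an extension of the scheme for the second. A later analysis plan cannot recover the distinction, because the reasons are collected as one tick.

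**Working it through.** The protocol states no figure for these items, so there is none to reproduce. The check compares wording and then asks what the answers can identify.

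**1. Question against answers**

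| | Gynecologists, item 9 | Other form, item 7 |
|---|---|---|
| Question asks | optimal | suitable |
| Yes affirms | usable | applicable |
| Scope of question | management before and after birth | the same |
| Scope of Yes | risk stratification, fetuses | risk stratification, patients |
| No affirms | complexity and incomplete coverage | the same |

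In item 9, Yes is weaker than the question (usable against optimal) and narrower (fetal risk stratification against management across birth). In item 7, *applicable* is close to *suitable*, although Yes is still limited to risk stratification. The two forms also ask different questions, so a difference in Yes shares between the groups could reflect wording rather than opinion.

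**2. What the No share identifies**

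Among respondents with a view, let the shares be:

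- *a*: neither objection
- *b*: complexity only
- *c*: coverage only
- *d*: both

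The share objecting to complexity is *b* + *d*, and the share objecting to coverage is *c* + *d*. Let *q* be the observed No share, and suppose that those with both objections choose No and those with neither do not.

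- *If every one-objection respondent chooses No:* *q* = *b* + *c* + *d*. Then *b* + *d* can lie anywhere from 0 to *q*, and so can *c* + *d*. They cannot both be 0, because their sum is *q* + *d*.
- *If respondents read* and *literally, so that only those with both choose No:* *q* = *d*. Each objection is then held by at least *q*.
- *If one-objection respondents scatter over the three answers:* *q* lies between *d* and *b* + *c* + *d*, and the share objecting to complexity may be below or above *q*.

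As an illustration only, take *q* = 40%, which is an assumption. The first case gives 0 to 40% for each objection, and the second gives at least 40% for each. The data do not show which case applies. A larger sample estimates *q* more precisely but does not narrow these ranges.

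**3. Whether another item fills the gap**

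| Reason in the literature review | Asked elsewhere? |
|---|---|
| Missing standards | Gynecologists' item 7; other form item 8 |
| Unfamiliarity or non-use | Gynecologists' item 8; other form item 6 |
| Information flow and cooperation | Gynecologists' item 6; other form items 5 and 9 |
| Complexity against coverage | No |
| Failure to predict some anomalies | No |

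The first three are at least touched on elsewhere. Nothing separates complexity from coverage.

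**The case against.** The strongest reply is that little depends on these items. The survey is described as one of awareness and current practice, and ranking barriers to UTD is not among its stated aims. The primary goal, prediction of a severe postnatal course and surgery, does not use the answers. An undivided No share is still a valid description if it is reported as worded, and item 9's Yes can be reported in its own words. All of this stands, and it limits the weight of the point.

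Three stronger readings are tempting but not supported:

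- **That the survey cannot identify any barrier to UTD.** Other items cover standards, familiarity and information flow. What is lost is complexity against coverage.
- **That the care model will rest on these answers.** The Introduction says only that the model is created after the other steps. No text says that these items feed it or that it must remove a barrier they reveal.
- **That a No share of *q* bounds each objection between 0 and *q*.** This holds only if every one-objection respondent chooses No. It cannot be assumed, since such a respondent has no accurate answer and may choose any of the three.

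The mismatch between question and Yes should not be charged equally to both forms. It is clear in item 9 and slight in item 7.

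The reply does not remove the core fault. The answers are fixed in the protocol, the two reasons are separate by its own account, and no analysis can split them afterwards.

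**Conclusion.** The point holds in a limited form. On both forms the only No joins two objections that the protocol lists separately, so the survey can neither separate complexity from incomplete coverage nor give a clean No share. On item 9 alone, a Yes share cannot be reported as the share who find UTD optimal. The differing questions on the two forms also weaken comparison between the groups.

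No numerical size can be given, because the protocol states no expected shares and any range for the two objections depends on how one-objection respondents answer. The reach is one item of ten on the gynecologists' form and one of nine on the other. The prediction goal is unaffected. This is a minor point, worth acting on because the survey is the first listed scientific goal and the correction costs little. It assumes that the online forms match the printed text, with no free-text field added.

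**What to change.** On both forms, use one common question about UTD with three plain answers: Yes, No, cannot comment. Yes should affirm exactly what the question asks. Respondents who choose No then get one tick-all follow-up: too complex; does not cover all dilations; other reason. Standards and familiarity need not be repeated there, since other items already ask about them.

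The cost is one reworded item and one short follow-up on each online form, so slightly more to fill in.

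The forms may already be in use: the stated study start is January 2023, the document is dated 19.12.2023, and it does not say when the survey is sent out. If they are in use, leave the data as collected. Report No as an undivided objection, report item 9 Yes as *usable* in fetal risk stratification, show the two groups' answers beside their own questions, and draw no conclusion on which reason dominates.

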Urinary Tract Dilations in Prenatal and Postnatal Life

ID: 0292/21/2023-00590

[name] [name], PhD.

19.12.2023

Study protocol

Brief Title

Urinary Tract Dilations in Prenatal and Postnatal Life

Director of study and central contact person

[name] [name], PhD.

Main sponsor

SonoClinic, s.r.o, [name]

Workplaces collaborating on the project

Emporia, s.r.o., [name]

NefroSa s.r.o., [name]

Solvers

[name] [name], PhD.

[name]. [name]., MPH

[name]

Scientific goals of the study

1. Multidisciplinary survey on awareness, state of diagnosis and management of patients with dilatation of the urinary tract.
2. The primary goal is the prediction of severe postnatal course and surgical intervention in fetuses with dilatation of the urinary tract according to the UTD classification from 2014.
3. The secondary goal is the creation of a model proposal for prenatal and postnatal care of a patient with dilatation of the urinary tract.

Duration of the study

Study start: january 2023

Study completion: june 2026

Introduction

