Parenchymal thickness Parenchymal appearance		Normal/Abnormal Normal/Abnormal	Subjective assessment Evaluate echogenicity, corticomedullary differentiation, and for cortical cysts
Ureter		Normal/Abnormal	Dilation of ureter is considered abnormal; however, transient visualization of the ureter is considered normal postnatally
Bladder		Normal/Abnormal	Evaluate wall thickness, for the presence of ureterocele, and for a dilated posterior urethra

A normal finding on the kidneys prenatally and postnatally is considered if the APD of the pelvis is less than 4 mm until the 28th week, less than 7 mm from the 28th week until the due date and less than 10 mm postnatally. A normal kidney does not have dilatation of the calyces,

the thickness and echogenicity of the parenchyma is normal, the ureter is not visible and the bladder has a normal image. Oligohydramnios is not present.

[figure not shown]
If dilation of the urinary tract is diagnosed prenatally, the finding is classified as low-risk UTD A1 or high-risk UTD A2-3 (table 2).

Table 2. Prenatal findings and risk stratification (Nguyen 2014).

If dilatation of the urinary tract is detected or persists postnatally, the risk group P1-P3 is determined based on the USG examination of the newborn, which is carried out at least 48 hours after birth (Table 3).

[figure not shown]
Table 3. Postnatal findings and risk stratification (Nguyen 2014).

Recommendation 4 – proposed management scheme:

[figure not shown]
Based on prenatal and postnatal USG findings, management is suggested in the care of a patient with urinary tract dilation. If during the US examination in the third trimester (32th week and more) an adjustment of the finding to the norm is detected (pelvis without dilatation, no changes in the kidney tissue), no further control is necessary. If the dilation persists in the third trimester, the following procedure is determined according to the degree of severity of UTD A1 or UTD A2-3 (table 4).

Table 4. Management of a fetus with dilatation of the urinary tract (Nguyen 2014).

When dilation of the urinary tract is found postnatally, the management is adapted and adjusted individually according to the workplace. It depends on the degree of severity P1-P3 (table 5).

Table 5. Management of a child with urinary tract dilatation (Nguyen 2014).

The choice to utilize prophylactic antibiotics or recommend voiding cystourethrogram will depend on the suspected underlying pathology

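### Item 10 of the gynecologist/sonographer questionnaire has no answer option that agrees with the protocol's own normal limits for renal pelvis width

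*Protocol*

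**What the plan says.** The first scientific goal in the protocol is a "Multidisciplinary survey on awareness, state of diagnosis and management of patients with dilatation of the urinary tract". The two questionnaires are printed in full under the methodology heading, so their wording is fixed in this document.

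Item 10 of the questionnaire for gynecologists and prenatal sonographers asks: "What are the normal values of renal pelvis width (APRPD) in the second, third trimester and postnatally". The three options are:

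- "a) 4-7 mm, 7-10 mm, over 10 mm"
- "b) Up to 4 mm, 4-7 mm, 10 mm"
- "c) 4-5 mm, 7-8 mm, 10 mm"

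The protocol defines a normal finding itself, in the literature review under Recommendation 3 (classification system), just after the table of ultrasound parameters. For the renal pelvis the prenatal limits are "less than 4 mm until the 28th week, less than 7 mm from the 28th week until the due date", and the limit after birth is "less than 10 mm postnatally".

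**The concern.** The item and the definition cover the same quantity in the same three periods. The study design places the third-trimester scan after week 28, so the item's trimesters match the definition's week-28 boundary. A respondent who knows the limits as the protocol states them should therefore find them among the options, and does not.

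The other items in both questionnaires ask about frequency of contact, practice, self-reported use of a classification, or opinion. Item 10 alone has an answer that can be right or wrong. It is thus the survey's one objective check on awareness, and an error in its options cannot be offset by another item. At stake is how far the answers to this item can be read as knowledge of the limits.

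**Working it through.** No sample size, power or error rate is involved. The check compares intervals.

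**Reference ranges** (protocol, Recommendation 3): 0 to under 4 mm before week 28; 0 to under 7 mm from week 28 to term; 0 to under 10 mm after birth.

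**Measure.** Share of the normal range covered = length of overlap between option and normal range ÷ length of normal range.

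| Option | Second trimester | Third trimester | After birth |
|---|---|---|---|
| (a) 4–7 / 7–10 / over 10 | 0/4 = 0% | 0/7 = 0% | 0/10 = 0% |
| (b) up to 4 / 4–7 / 10, read literally | 4/4 = 100% | (7 − 4)/7 = 3/7 ≈ 43% | 0/10 = 0% |
| (c) 4–5 / 7–8 / 10 | 0/4 = 0% | 0/7 = 0% | 0/10 = 0% |

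**Options (a) and (c).** Every value lies at or above the protocol's limit in every period. Neither describes normal widths at any of the three times.

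**Option (b).**
- Second trimester: it matches, apart from the boundary. Up to 4 mm can include 4 mm itself, which the definition does not.
- Third trimester: the upper end, 7 mm, is right. The lower end of 4 mm is not in the definition, and it excludes 0 to under 4 mm, that is 4/7 ≈ 57% of the normal range.
- After birth: a single value of 10 mm is not a range and is not below 10 mm. Option (c) gives the same figure, so this part of the answer cannot separate (b) from (c).

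**Option (b) read as upper limits only.** If the reader ignores the lower bound of 4 mm and takes the bare 10 mm as a maximum, (b) gives 4, 7 and 10 mm and agrees with all three cut-offs. Neither (a) nor (c) can be read this way, since their upper ends before birth are 7 and 10 mm, and 5 and 8 mm.

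**Result.** As written, 0 of 3 options agree with the definition in all three periods. Option (b) comes nearest and is the only one whose upper ends are the protocol's three limits.

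**The case against.** The strongest reply is that (b) does its job. The stem asks for normal values, (a) and (c) fail in both prenatal periods, and a respondent who knows 4, 7 and 10 mm as upper limits is steered to (b). This stands in the main. A reader might infer that informed respondents would scatter over the options and be scored unreliably, and the document does not support that. One qualification remains: the figures 4, 7 and 10 occur in order in all three options, as starting points in (a) and (c) and as end points in (b), and (b) mixes three notations. Some ambiguity is therefore in the text, but nothing shows that it would move many answers.

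A reader might also infer that respondents who do not know must guess, and that the share of right answers is inflated as a result. This should not be claimed. The protocol says only that the form is made with an online tool, not that answers are mandatory. Inflation by guessing would also affect any three-option item without a don't-know answer, however well keyed, so it does not measure this mismatch.

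Third, the protocol states no answer key, knowledge score or percent correct, and it describes the survey as collecting information on methods, classification and management. Awareness of the UTD system is also asked directly, in item 8 of the first questionnaire and item 6 of the second. Both points hold and limit the consequence. A reader might infer that the error carries through to the care model, but the protocol ties that model to no survey item, and its stated primary goal is prediction.

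Finally, the English text is uneven, and the form that respondents saw may be worded differently. That is possible, but the document at hand does not show it.

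**Conclusion.** The point holds as a minor instrument error. The options of item 10 contradict the protocol's own definition of normal: none agrees with it in all three periods, and the probable key is wrong as worded in two of them (third trimester and after birth). The effect is confined to one item in one of two questionnaires, and the prediction goal is untouched.

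No size can be given for any distortion of the survey results, because the protocol does not say how the item is keyed, scored or reported. That (b) is the intended key is an assumption, based on its being the only option with 4, 7 and 10 mm as its upper ends. The comparison takes the protocol's definition as the reference because it is the document's own statement. It is not a judgement on which limits are clinically right.

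**What to change.** Reconcile item 10 with the definition under Recommendation 3:

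- Ask for the upper limit of normal renal pelvis width before week 28, from week 28 to term, and after birth.
- Write all options in one form (under x mm), with one option identical to the protocol's three limits.
- State in the protocol which option is the key.
- Optionally, add an answer for respondents who do not know.

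The cost is an edit to one item of an online form. The protocol is dated December 2023 and gives January 2023 as the study start, so answers may already have been collected. In that case, check the wording actually shown to respondents, report the distribution over the three options, and do not report a percent correct. That costs only a restriction on reporting.
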